2 STUDY OBJECTIVES

The purpose of the study is to demonstrate feasibility of conducting a field trial of cellphone blocking technology in teen drivers to calculate sample sizes for future trials and generate preliminary data for funding applications. Primarily, the proposed is measuring whether activation of a cellphone blocking device results in a decrease in the total proportion of time in which a cellphone is being used at non-zero speeds by teen drivers.

2.1 Primary Objective (or Aim)

The primary objective of this study is to determine the feasibility of conducting an on-road driving study studying cellphone blocking technologies.

2.2 Secondary Objectives (or Aim)

The secondary objectives are to:

- Measure whether activation of a cellphone blocking device (DriveID) results in a decrease in the total proportion of time in which a cellphone is being used at non-zero speeds by teen drivers compared with baseline cellphone use while driving.
-

- Measure the reasons cellphones are being used while driving at non-zero speeds among teens (calls, texts, smartphone apps, etc.)
- Measure teen satisfaction with the cellphone monitoring and blocking device
- Determine the incidence of handheld cellphone use while driving and its relationship to incoming text messages and driving conditions in a teen driver cohort.
- Measure the number of phone unlocks per hour of drive time
- Measure the speed of the car, acceleration, and spatial characteristics of phone unlocks (ex. on highways vs. at intersections)

3 INVESTIGATIONAL PLAN

3.1 General Schema of Study Design

This is a randomized control study of control vs. cellphone blocking conditions.

3.1.1 Screening Phase

Participants will also be recruited through posted flyers, postcards, email blasts, through the Recruitment Enhancement Core (REC), social media, and by word-of-mouth/colleague referrals at Penn and CHOP. The flyers will be posted in a variety of public and private locations, including but not limited to, local public and private high schools in suburban and local Philadelphia, summer camps, universities, etc. No recruitment will occur through schools or public places without first obtaining permission. Postcards will be mailed to potentially eligible families identified by the REC and the Penn Social Media & Health Innovation Lab.

The Penn Social Media & Health Innovation Lab will assist with recruitment through a variety of social media outlets including Facebook and Craigslist. Language for these postings have been included with the application.

Interested participants will be directed to the Way to Health platform. A parent will create an account and consent online. Once consent is obtained, teens will be able to create their own account and assent online. Once consent and assent are obtained, teens will be screened for eligibility with an eligibility survey presented on the Way to Health platform. Only eligibility criteria will be asked. If a participant responds “yes” to all questions, teens will be presented with an intake survey on the Way to Health platform. Questions will cover demographics, opinions, perceptions and experiences with texting and driving. The teen will be asked to email the study team a picture of their driver’s license. A member of the study team will also contact the teen to answer any questions and to mail out the CellControl device. If a teen is not eligible, the participant will be informed that they are ineligible for the current study.

If participants turn 18 during the duration of the study, they will be re-consented as an adult through Way to Health.

3.1.2 Baseline Measurement Period (4 Week Block)

DriveID will monitor all cellphone use while the teen driver's cellphone is in the car in which DriveID is installed. The application will run in the background, so there will be no observable changes to participants' cellphone functions. DriveID will capture GPS data throughout the baseline, intervention, and follow-up periods. At the completion of the fourth week, the teen participant will be instructed to complete an online survey administered through Penn's Way to Health IT platform asking about driving behaviors for the first thirty days of the study. Participants will have 2 weeks to complete this survey.

3.1.3 Intervention Period (4 Week Block)

At the beginning of the intervention period (this will start within 2 business days of baseline measurement period survey completion), all participants will receive an email with a link to an educational website that raises awareness of the dangers of distracted driving (<http://endddd.org>). The Children's Hospital of Philadelphia has performed an independent evaluation of the educational content of the website and found it to be evidence based, and scientifically guided⁸.

DriveID will be used as a cellphone blocking device for those in the three cellphone blocking conditions where the phone will lock while driving, but the locking function can be overridden according to pre-set settings. DriveID will continue to monitor cellphone use while driving including how often the teen unlocks the cellphone as well as if they are using the phone for a call or other phone features. However, DriveID is not able to differentiate which phone features are being used.

The study team does not promote texting and driving and encourages all participants to drive safely.

3.1.4 Follow-up Period (2 Week Block)

At the end of the intervention period, participants will be able to choose a configuration of the Cellcontrol (no blocking, opt-in blocking, opt-out blocking, and opt-out blocking with parental notification). Participants will have up to 1 week to choose mode (via phone call, survey on Way to Health, or via text message). If a participant does not choose mode, the setting will default to remain in what setting the participant was randomized to for the intervention period. We will continue to measure our primary and secondary endpoints. At the completion of the follow-up period or upon voluntary withdrawal from the trial, the teen participant will be instructed to complete an online survey administered through Penn's Way to Health IT platform asking about user satisfaction with the device and its configurations. Members of the study team may also contact the teen participant to participate in a semi-structured phone interview conducted by a member of the study team. The interview will be audio recorded.

3.2 Allocation to Treatment Groups and Blinding

Participants will be randomized to one of four groups. The randomization chart will be maintained on a secure server that is only accessible by key study personnel. Participants and study staff will be aware of which group they have been assigned to. A minimum of five participants will be enrolled into each group.

3.3 Study Duration, Enrollment and Number of Sites

3.3.1 Duration of Study Participation

The study duration per subject will be approximately 3 months , with up to four weeks of Phase 1 (baseline period), up to four weeks Phase 2 (intervention period), and up to two weeks Phase 3 (follow-up period).

3.3.2 Total Number of Study Sites/Total Number of Subjects Projected

The study is being conducted at the Children’s Hospital of Philadelphia and the University of Pennsylvania. It is expected that up to 250 people will participate in this research study.

3.4 Study Population

3.4.1 Inclusion Criteria

- 1) High school student (16 or 17 at start of the study)
- 2) Holds a valid driver’s license
- 3) Lives in parent/guardian’s home
- 4) Drives an average of 4 trips per week
- 5) Primarily drive one car
- 6) Has their own iPhone 4S or newer or Android 4.3 or newer smartphone with data plan
- 7) Parent/guardian is willing to assist with installation
- 8) Admits to texting while driving at least once in the last month

3.4.2 Exclusion Criteria

- 1) Already uses a smartphone app or hardware device to limit cellphone use while driving

Subjects that do not meet all of the enrollment criteria may not be enrolled. Any violations of these criteria must be reported in accordance with IRB Policies and Procedures.

4 STUDY PROCEDURES

4.1 Screening Procedure and Online Consent/Assent Process

Potential participants will either be recruited directly from the eligible participant pool surveyed under IRB protocol (#14-11072) or they will be recruited through methods discussed in section 9.5. Eligible participants from the previous survey study will be contacted by study team members with information about the study. Interested participants outside of that study will be directed to the Way to Health Platform to get more information on the trial and complete the online consent/assent process.

Teens and parents will be instructed that the parent first needs to create a username and password, and create a profile through the WTH platform and then review a consent and sign prior to their teen being screened for the trial. The profile on Way to Health asks for parent's contact information and date of birth. We are not collecting this as data, but it is required in order to create a WTH profile. After a parent consents for their teen to participate they will be instructed to have their teen go to the WTH site and register. Teens will then review and sign an assent for the trial. Following this they will be screened with an eligibility survey presented on the WTH platform. If a participant responds "yes" to all questions they will be allowed to continue in the trial and will be asked to complete the intake survey immediately. Questions will cover demographics, opinions, perceptions and experiences with texting and driving. They will then continue on with their trial participation. If they are not eligible, the participant will be informed that they are ineligible for the current study and will not complete any study procedures. These teens will be documented as screen failures

Teens will be asked to email the study team a copy of their driver's license. A member of the study team will then contact the teen and parent/guardian to schedule an in person meeting or a phone meeting. During this meeting the study team will answer any questions pertaining to the consent or the study and distribute the DriveID device in person or by mail. If a participant turns 18 years old during their participation in the study, a member of the study team will email the teen a link to complete the online consent via WTH in order to re-consent. Participants will receive an email or a text message reminder regarding incomplete steps in WTH depending on their preference selection for communication.

The validation of the online consent/assent process will be met during this meeting and allow for the fulfillment of one of the study aims: to demonstrate the feasibility and effectiveness of an online consent process in order to remotely recruit a larger number of participants in future studies among those who purchase the Cellcontrol product. During the meeting, a member of the study team will ensure that the participants truly understand the risks and benefits of the study. If any participants wish to withdraw, they may do so at this time.

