6.2 Secondary Endpoints

Total proportion of time the phone is in use at non-zero speeds

Seconds of phone use at non-zero speeds

Seconds of phone use while stopped

Number of incoming calls and texts that were blocked

Number of times participants make or receive a phone call, send or read a text message, and use any application while driving at non-zero speeds

Proportion of participants who switched to another blocking configuration in the Follow up period

Participant acceptance of cellphone blocking technology based on post-study survey

Incidence of handheld cellphone use and its relationship to incoming text messages and driving

In determining feasibility the following will be measured:

- Proportion of screen eligible who enroll
 - Number enrolled per month
 - Retention rates by study arm
 - Proportion of surveys completed
-

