9.6 Informed Consent/Assent

We will require parental consent and teen assent for this trial. Parental consent and subject assent for this trial will be obtained via Way to Health.

Interested participants will be directed to the Way to Health Platform to get more information on the trial and complete the online consent/assent process.

Teens and parents will be instructed that the parent first needs to create a username and password through the WTH platform and then review a consent and sign prior to their teen being screened for the trial. After a parent consents for their teen to participate they will be instructed to have their teen go to the WTH site and register. Teens will then review and sign an assent for the trial.

A member of the study team will then contact the teen and parent/guardian to schedule an in person meeting or a phone meeting. During this meeting the study team will answer any questions pertaining to the consent or the study and distribute the DriveID device in person or by mail. If a participant turns 18 years old during their participation in the study, a member of the study team will email the teen a link to complete the online consent via WTH in order to re-consent. Participants will receive an email or a text message reminder regarding incomplete steps in WTH depending on their preference selection for communication.

The validation of the online consent/assent process will be met during this meeting and allow for the fulfillment of one of the study aims: to demonstrate the feasibility and effectiveness of an online consent process in order to remotely recruit a larger number of participants in future studies among those who purchase the Cellcontrol product. During the meeting, a member of the study team will ensure that the participants truly understand the risks and benefits of the study. If any participants wish to withdraw, they may do so at this time.

A member of the study team will contact all enrolled participants to ensure understanding of study procedures. Electronic signatures will be obtained for both parent and child.

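### The aim of showing that online consent is effective has no measure of understanding before the staff meeting named as its validation, and no criterion by which it could fail

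*Combined protocol and SAP*

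**What the plan says.** Section 4.1 (Screening Procedure and Online Consent/Assent Process) and section 9.6 (Informed Consent/Assent) carry the same paragraph. It names as a study aim "to demonstrate the feasibility and effectiveness of an online consent process", with a view to remote recruitment of larger numbers in later studies. On how the aim is met, it says: "The validation of the online consent/assent process will be met during this meeting".

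The meeting is held in person or by phone, after parent and teen have signed online. Its content is given in three statements:
- "During this meeting the study team will answer any questions pertaining to the consent or the study".
- On understanding: "a member of the study team will ensure that the participants truly understand the risks and benefits of the study".
- Families who no longer want to take part can leave the trial at that point.

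Section 9.6 adds a further contact: "A member of the study team will contact all enrolled participants to ensure understanding of study procedures".

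Section 6.2 introduces its feasibility list with "In determining feasibility the following will be measured". The four items are the share of screen-eligible teens who enrol, enrolment per month, retention by arm, and survey completion.

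**The concern.** Whether online consent is effective depends on what parent and teen understood when they had signed online and before staff explained the study to them. The meeting comes later and is designed to close any gap in understanding. The event named as the validation is therefore also the event that corrects a failure of the process being validated. What families understand at the end of it cannot be credited to the online step.

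This matters because the trial is a pilot meant to inform later studies, and the aim is written to support remote consent on a larger scale. The participants are 16 or 17 years old. First-attempt understanding also cannot be recovered once staff have spoken to the family.

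**Working it through.** The documents give no sample size, rate, threshold or test for this aim, so there is no figure to reproduce. The check is a trace through the text, followed by a short illustration.

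**1. Order of events (section 4.1).** Parent account and online consent; teen registration and online assent; eligibility survey; intake survey for those eligible; copy of the driver's licence sent; meeting with staff. Understanding is first mentioned at the last step.

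**2. Where a measure of the aim could sit.**
- Sections 2, 2.1 and 2.2 (objectives): online consent does not appear.
- Section 6.1 (primary endpoint): phone unlocks per hour.
- Section 6.2 (secondary endpoints): phone use, blocked calls and texts, choice of configuration, and acceptance of the technology. None concerns consent.
- Section 6.2 (feasibility list): four operational items, none on understanding. The closest is the share of screen-eligible teens who enrol. Screening follows consent and assent, so everyone in that denominator has already completed the online step. The item cannot show drop-out or failure at that step.
- Sections 5.2, 5.4, 5.5 and 5.6 (intake, post-baseline and end-of-study surveys, and the interview): the listed content does not include understanding of the consent.
- Section 6.3.2 (analysis): covers unlocks per hour only.

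**3. What could count as failure.** The only negative event described at the meeting is voluntary withdrawal, and it is not tied to any criterion for the consent process. No group consents without staff contact.

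**4. What the end of the meeting says about the online step (all values assumed).** Let p be the share who understand after the online step alone, and c the share of the remainder whom staff bring to understanding. Understanding at the end of the meeting is p + (1 − p)c.
- c = 1, the literal sense of ensuring understanding: p + (1 − p) = 100% for every p from 0 to 1.
- c = 0.9, p = 0.3: 0.3 + 0.7 × 0.9 = 93%.
- c = 0.9, p = 0.9: 0.9 + 0.1 × 0.9 = 99%.

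A 60-point difference in p shrinks to 6 points after the meeting when c = 0.9, and to none when c = 1.

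**5. What a direct measure would give.** Section 3.2 sets a minimum of five participants in each of four groups, so 4 × 5 = 20. Section 3.3.2 projects up to 250. If 70% passed at first attempt (an assumed value, to show precision only), the exact (Clopper-Pearson) 95% interval would be 45.7% to 88.1% for 14/20 and 63.9% to 75.6% for 175/250. Assignment happens when participants reach the intervention phase (section 9.1.1), whereas consent precedes screening, so consenting families would number at least 20 and probably more.

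**The case against.** The strongest reply has five parts.

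First, the meeting is a sound protection for minors, and every enrolled participant is contacted. That stands. A reader might infer that participants are poorly protected in this trial, and the documents do not support that.

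Second, no decision rule is written down. A reader might infer that the trial will declare online consent effective whatever happened online, or that it will overstate understanding by some number of points. The wording that validation will be met invites this reading. However, the documents promise no conclusion and plan no comprehension percentage, so neither inference is established. What the text shows is narrower: the aim has no criterion by which it could fail.

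Third, staff might probe understanding before explaining, and the online flow might contain a check. The meeting text neither describes nor excludes probing, and the consent pages are not in the text available here. The finding is therefore limited to what the available text describes.

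Fourth, operational feasibility is partly measured through enrolment per month, the share of eligible teens who enrol, and documented screen failures. Section 4.3.4 also asks those who withdraw early why they did so. This stands, and it confines the gap to effectiveness in the sense of understanding.

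Fifth, the aim is peripheral: it is absent from the objectives and endpoints. That limits its weight. It does not remove the problem, because the protocol twice calls it a study aim and ties it to later trials.

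**Conclusion.** The point holds in a limited form. As written, the trial cannot support the claim that online consent is effective, because the stated validation takes place where staff secure understanding, and no earlier measure or success criterion is described. The feasibility part of the aim is partly covered by section 6.2. The randomised comparison of unlocks per hour is unaffected.

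No numerical size can be given for the defect, since the documents contain no figure for understanding. The illustration with p and c shows only that the result at the end of the meeting is nearly uninformative about the online step when staff correct most gaps. It rests on assumed values of both. The conclusion also assumes that the consent pages, not seen here, contain no scored check.

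**What to change.** 1. On Way to Health, immediately after e-signature and before the staff meeting, give parent and teen a short fixed comprehension check and store the first-attempt score.
2. Add two feasibility measures to section 6.2: the proportion passing at first attempt (parents and teens separately), with a success threshold set in advance, and the proportion withdrawing at the meeting. Choose the threshold with the intervals above in mind: near the minimum size, only a coarse criterion can be judged.
3. Report participants from the IRB #14-11072 pool separately. Section 4.1 has study team members contact them with information about the study beforehand, so their scores do not reflect the online process alone.
4. Keep the meeting as a safeguard.

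If this is not done, delete effectiveness from the aim in sections 4.1 and 9.6, and describe the meeting as a safeguard and not as a validation.

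Cost: a few items on the existing platform, one or two minutes per participant, and an IRB amendment. The alternative needs only a wording change.

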4.2 Device Installation

Parents will install the DriveID device for the teen participant via instructions provided with the device. The DriveID device is installed behind the rearview mirror as to not impede vision of the road; the size of the device is approximately 3 inches by 5 inches. The parent and teen will also complete online registration of the device. When installation is completed correctly, a confirmation message is sent to Cellcontrol. If Cellcontrol receives an error message, noting incorrect installation, a member of the study team will contact participants to troubleshoot.

4.3 Study Treatment Phase

The study treatment phase will consist of three parts: a baseline measurement period, an intervention period, and a follow-up period.

4.3.1 Baseline Measurement

DriveID will measure participants' cellphone use while the cellphone is in the car in which the DriveID device is installed. DriveID will also record GPS data. This data will not be accessed in real time by the study team and will only be viewed after the completion of the drive. The participants will not have access to the usage data during the baseline period and will have no interaction with the device as the monitoring occurs.

Coded data on primary and secondary endpoints will be automatically uploaded daily whenever the phone has a Wi-Fi or cellular data connection to the Cellcontrol server and then exported through an encrypted, secure internet connection to Penn's Way to Health IT Platform for management and analysis via linkage of a study ID.

